8.1. Observations and tests

Each endpoint in this study is presented below. All data required by the protocol should be recorded.

Table 8.1 Observations and tests

Treatment compliance	Doses of lenvatinib and pembrolizumab, date of first dose, date of last dose or date of discontinuation (treatment interruption), presence/absence of dose change and its reason, and presence/absence of treatment interruption, its frequency and its reason
Patient background characteristics	Sex, age, past history, complications, histology (pap, tub1, tub2, por1, por2, sig, muc or other), HER2, EBV, PD-L1, presence or absence of the primary lesion, lesion site (primary site, target lesion, nontarget lesion) and presence or absence of previous treatment and its details
Physical examination	Body height and weight
Vital signs	Body temperature, pulse rate, systolic and diastolic blood pressure
General condition	PS(ECOG)
AEs	Presence/absence and severity of AEs will be evaluated in accordance with the CTCAE v 4.0.
Concomitant medications/therapies	Name of drug, route of administration, start date of treatment, end date of treatment and reason for concomitant use
Hematology	Red blood cell count, Hb, hematocrit, White blood cell count, neutrophil count, and platelet count
Biochemistry	AST(GOT), ALT(GPT), ALP, LDH, albumin, total bilirubin, BUN, creatinine, CK, electrolytes (Na, K, Cl, Ca), Amy, UA, blood glucose, CRP
Blood coagulation test	PT, INR, APTT
Thyroid function	Thyroid stimulating hormone, free triiodothyronine (fT3), and free thyroxine (fT4)
Tumor markers	CEA, CA19-9
Urinalysis	Urine protein, urinary sugar and urinary occult blood
Pregnancy test	If pregnancy is suspected by urinalysis, a serum test It will be performed in premenopausal women or women who had the last menstruation no more than one year
ECG	12-lead resting ECG
Infection	HIV antibody, HBs antigen, HBC antibody, HBs antibody, HCV antibody, HBV-DNA

Tumor assessment	
Chest and abdomen/pelvic contrast CT* or abdomen/pelvic contrast MRI*, as necessary, chest radiography, brain CT and brain MRI
 
* For patients who are allergic or have hypersensitivity to contrast media to be used for CT and MRI, the tests may be performed without using the contrast media.
 
When the treatment is discontinued because of reasons other than the progression of the primary disease based on imaging, the assessment should be made until progression is confirmed.

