8.6. Tumor evaluation

For all patients, tumor evaluations will be conducted using the irRECIST and RECIST guidelines version 1.1. Tumor evaluations of the chest, abdomen, and pelvis (when deemed clinically necessary) will be conducted at each time point listed below until an exacerbation is confirmed. Thoracoabdominal and pelvic contrast-enhanced CT or MRI will be performed (if the subject is allergic to the contrast medium, plain scans are permitted).

- Less than 21 days before enrollment in this trial

Evaluations will be performed in weeks 6, 12, 18, and 24 after the beginning of treatment (followed by every 9 weeks until week 42, then every 12 weeks thereafter).

- When treatment is terminated for reasons other than an exacerbation of the underlying disease on imaging, an evaluation will be performed within 2 weeks of dosing completion. Furthermore, tumor evaluations are to be conducted in accordance with the schedule until an exacerbation of the underlying disease is confirmed, or until commencement of a new anticancer treatment.

The principal investigator and radiologist will conduct tumor evaluations in accordance with the irRECIST and RECIST guidelines version 1.1 (refer to appendices 2 and 3). The decision to continue the investigational drugs will be determined on the basis of these evaluations, including the effects on target and nontarget lesions and the appearance of new lesions. When disease progression is first observed on imaging in clinically stable patients according to irRECIST, participating medical institutions will conduct repeat scans 4 weeks after the initial identification of disease progression via an image evaluation to determine disease progression. Administration of the investigational drug can continue until the repeat scan is conducted (refer to Table 8.6). The criteria for clinical stability are listed below.

- Absence of clinical signs and symptoms indicating disease progression.
- No worsening of ECOG PS.
- No sudden disease progression observed
- Absence of tumor enlargement in the main anatomical site requiring new emergency medical intervention (e.g., spinal cord compression).

Furthermore, in the present trial, a maximum of 5 lesions can be included as target lesions, with a maximum of two lesions per organ.

Table 8.6: Imaging and investigational drug dosing after disease progression is first observed on imaging

	Clinically stable		Clinically unstable	

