11.2.2. Progression free survival:PFS

The period will be from the day of enrollment, as the starting date of the computation, to the day when progression is determined or the day of death of any cause, whichever comes earlier.

- “Progression” will be PD based on diagnostic imaging according to overall response by RECIST v1.1. The day of the imaging test will be defined as the day of progression. When the treatment are discontinued due to clinical PD and diagnostic imaging can not be performed, the day of clinical PD will be defined as the day of progression.
- Surviving patients, who are not assessed as progression will be censored on the last day when no progression is confirmed on imaging (last day of PFS confirmed) (If information on progression or progression-free is obtained from medical institutions to which the patients are transferred or referred, a statement on medical information provision documenting the rationales for a diagnosis should be received and retained. Notification only by telephone will not be acceptable.).
- For patients who died without being assessed as progression, whether to consider to be an “event on the day of death” or “censoring on the last day of PFS confirmed” should be decided at the time of data review performed prior to data fixation. In principle, they should be “an “event on the day of death” unless the period from the last day of PFS confirmed to the day of death is long.
- When another treatment is given as subsequent treatment in withdrawals due to AEs or refusal, they should be censored on the start day of the subsequent treatment.
- The development of secondary cancer (asynchronous double cancer) should not be handled as an event or censoring but as PFS until other events are observed.

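### PFS for patients who leave for an AE or refusal is censored at the start of the next therapy and not at the last scan: a small, one-way upward bias in a secondary endpoint

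*Combined protocol and SAP*

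**What the plan says.** Section 11.2.2 dates imaging progression by the scan: "The day of the imaging test will be defined as the day of progression". A clinical progression date is used only when treatment stops for clinical progression and imaging cannot be done. Two censoring rules matter here.

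- General rule (second bullet): "Surviving patients, who are not assessed as progression will be censored on the last day when no progression is confirmed on imaging".
- Rule for AE or refusal (fourth bullet), when another treatment follows: "in withdrawals due to AEs or refusal, they should be censored on the start day of the subsequent treatment".

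Section 8.6 governs scanning after a stop for reasons other than imaging progression. First, "an evaluation will be performed within 2 weeks of dosing completion". Scheduled scans then go on until progression "or until commencement of a new anticancer treatment". The schedule is weeks 6, 12, 18 and 24, "followed by every 9 weeks until week 42, then every 12 weeks thereafter". The synopsis (duration of study participation) also ends tumour follow-up at progression or new anticancer treatment, whichever is first. Table 8.1 mentions only progression: "the assessment should be made until progression is confirmed". Section 6.2.2 lets the investigator omit follow-up tests judged impossible or unnecessary.

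Section 6.2.1 lists further reasons for stopping without progression, such as physician judgement, including a need for other anticancer treatment (item 12). The fourth bullet of 11.2.2 does not name them.

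**The concern.** A PFS censoring date should be the last day on which the patient was known to be progression-free. Section 11.2.2 applies that standard strictly elsewhere: for transferred patients it asks for a written statement of the grounds for the diagnosis and does not accept a telephone report. The fourth bullet then credits an interval that no scan need cover.

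The convention also turns on the recorded reason for leaving, in an open-label trial. A patient who leaves for toxicity and one stopped by physician judgement may have the same scans and the same new-therapy date, yet receive different PFS times.

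The stake is the PFS estimate. It is secondary and descriptive, but 12.4 makes the judgement that the treatment is promising depend on improvement in the secondary endpoints as well as on ORR. With a single arm, PFS has no concurrent comparator that is handled in the same way.

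**Working it through.** **The plan's own figure.** The documents give no design figure for PFS. The only one to reproduce is the ORR design in 2.10.2: continue at 2 or more responses of 10, succeed at 6 or more of 29, threshold 10%, expected 30%. The success probability is the sum over x = 2 to 10 of P(Bin(10, p) = x) × P(Bin(19, p) ≥ 6 − x).

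- p = 0.10: 0.0471, within the one-sided 5%.
- p = 0.30: 0.8051, against 80% stated.

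The design reproduces, and PFS censoring does not enter it.

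**Direction.** At each event the Kaplan-Meier curve is multiplied by 1 − 1/n, where n is the number at risk. Moving a censoring date later leaves every event time where it was and can only add to n. One extra patient at risk changes the factor to 1 − 1/(n + 1), which is larger by 1/[n(n + 1)]. With an illustrative n = 15: 14/15 = 0.9333 against 15/16 = 0.9375, a difference of 1/240 = 0.0042. The curve under the start-date rule is therefore never below the curve under the last-scan rule. The two differ only if another patient has an event inside the credited interval.

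**Length of the interval.** If scans follow 8.6, the unscanned time is at most about 6 weeks up to week 24, 9 weeks up to week 42 and 12 weeks after that. The end-of-treatment scan often shortens it. It is longer only if scans are missed or waived. The synopsis and Table 8.2 give 6-weekly scans throughout, which differs from 8.6 after week 24 and changes this bound.

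**Size.** Simulated trials of 29 patients compared the two censoring dates.

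- From the documents: n = 29; the scan schedule in 8.6; enrolment-to-treatment delay of 0-13 days (from 6.1); and, as a planning value, median PFS of 5.6 months, or 24.3 weeks (the pembrolizumab plus ramucirumab figure in 2.7).
- Assumed: exponential PFS; 15% or 30% leave for AE or refusal and start new therapy; withdrawal uniform over weeks 3-30; new therapy 4 or 12 weeks later.

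| Scans after withdrawal | Mean shift in median PFS | Shift in 26-week PFS |
|---|---|---|
| End-of-treatment scan plus scheduled scans (8.6) | 0.2 to 0.8 weeks | 0.3 to 0.9 points |
| None | 1.0 to 4.8 weeks | 1.5 to 5.7 points |

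In the first row the median was identical under both rules in 80-92% of trials.

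A separate large-sample calculation assumed a scan at withdrawal and none afterwards, with median PFS of 3, 5 or 7 months, 10-30% leaving, and 2, 6 or 12 weeks to new therapy. Six-month PFS rose by 0.1 to 6.8 points, for example 1.3 points at 5 months, 20% and 6 weeks. The median hardly moved, because in large samples it sits on a scan date. With 29 patients it sometimes jumps to a later event, so the mean shift is not zero.

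**Other reasons for stopping.** A patient stopped under 6.2.1 item 12 who starts new therapy has no explicit rule. If imaging ends at new therapy (8.6, synopsis), the general rule gives the last scan. If it continues to progression, as Table 8.1 can be read, progression on the next therapy becomes a PFS event.

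**The case against.** Much of the case for leaving the text alone has force.

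- **A reader might infer that the two bullets contradict each other.** They need not. The fourth is most naturally a specific exception to the second. Precedence is unstated, but the ordinary reading gives one date.
- **A reader might infer that nobody looks at these patients after they stop.** Section 8.6 says otherwise: a scan within 2 weeks of the end of dosing, then scheduled scans until new therapy. Under the plan as written the gap is normally less than one scan interval.
- **A reader might take the shift of about 5 weeks as the expected size.** It requires that no withdrawn patient is scanned. Section 6.2.2 allows tests to be omitted case by case, not as a policy.
- **A reader might infer that other withdrawals are mishandled.** That rests on silence. The general rule already gives them last-scan censoring, which is the preferable outcome. Some examples are also remote: 35 three-weekly doses (item 10) take about two years. Item 12 is the realistic case.
- **A reader might count Table 8.1 as an equal rival to 8.6.** The synopsis agrees with 8.6, so a shorter table entry stands against two explicit statements. It still needs reconciling.
- **Detail may be elsewhere.** Section 12 defers data handling to a separately prepared SAP, whose text is not part of the material reviewed. It may cover these cases.
- **PFS carries no threshold or planned test of the treatment effect**, and the censoring rules behind any outside comparison figures cannot be seen here.

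What survives is narrower: the fourth bullet uses a date that is not an assessment, its effect has one sign, and its use depends on the recorded reason for leaving. None of the points above removes these.

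**Conclusion.** The concern holds as a small, one-way bias with low-to-moderate severity. The direction follows from the Kaplan-Meier arithmetic and needs no assumption. The size does: it rests on exponential PFS with a 5.6-month median, 15-30% leaving for AE or refusal and starting new therapy, and a delay of 4-12 weeks. The documents give neither the withdrawal fraction nor the delay. On those assumptions, and with the 8.6 scans done, median PFS rises by about 0.2 to 0.8 weeks on average and 26-week PFS by 0.3 to 0.9 points. Without off-treatment scans the figures are about 1 to 5 weeks and 1.5 to 6 points.

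The documents do not support calling this a contradiction in the PFS definition or a threat to the trial's main conclusion. The ORR test, the sample size and the error rates are unaffected.

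**What to change.** Replace the fourth bullet of 11.2.2, and any matching SAP text, with: *Patients who start any subsequent anticancer treatment before documented progression, for whatever reason, are censored at the last tumour assessment showing no progression on or before that start date.*

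Keep censoring at the start of subsequent treatment as a sensitivity analysis, so that the effect of the convention is visible. Reconcile Table 8.1 with 8.6 and the synopsis on when imaging ends. Reconcile the scan interval after week 24 between 8.6 on one side and the synopsis and Table 8.2 on the other.

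The cost is one sentence, one extra Kaplan-Meier run and a wording clean-up. No sample size or ORR rule changes. The downside is that reported PFS may come out slightly shorter.

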11.2.3. Disease control rate:DCR

The DCR will be defined as the proportion of patients who achieved CR or PR, or SD

for best overall response according to RECIST v1.1.

11.2.4. Overall survival: OS

The period will be from the day of enrollment, as the starting date of the computation, to the day of death of any cause.

Surviving patients should be censored on the last day of PFS confirmed (Confirmation of survival by telephone inquiry will be acceptable. However, the fact of confirming survival should be documented in medical records.).

Patients who are lost to follow up should be censored on the last day when their survival is confirmed before being lost to follow up.

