Investigation of outcome	
Presence or absence of subsequent treatment, if subsequent treatment is given, a treatment method and start date
 
Date of death or the last day of survival confirmed, and if died, the cause of death

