12. STATISTICAL MATTERS

The Statistical Analysis Plan is summarized below. The details are presented in the separately prepared “Statistical Analysis Plan.”

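### The OS censoring rule for survivors names the PFS imaging date, contradicts its own sentence, and would understate OS if progressed survivors were cut back to it

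*Combined protocol and SAP*

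**What the plan says.** For OS, section 11.2.4 counts from enrolment to death from any cause and then states: "Surviving patients should be censored on the last day of PFS confirmed". A parenthesis in the same sentence adds: "Confirmation of survival by telephone inquiry will be acceptable". The next sentence reads: "Patients who are lost to follow up should be censored on the last day when their survival is confirmed".

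The term used for survivors is defined in section 11.2.2, on PFS. That rule opens "Surviving patients, who are not assessed as progression will be censored on the last day" and fixes the day: such patients are "censored on the last day when no progression is confirmed on imaging (last day of PFS confirmed". For outside information on progression, the same bullet says: "Notification only by telephone will not be acceptable".

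Table 8.1 (section 8.1) lists, under the outcome investigation, "Date of death or the last day of survival confirmed". Section 8.7 follows outcome after treatment until death or up to 2 years after the last enrolment. Section 12 is a summary of a separate Statistical Analysis Plan: "The details are presented in the separately prepared" plan. That plan is not among the documents, so 11.2.4 is the only visible OS censoring rule.

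**The concern.** A PFS date is used to end OS follow-up. For a survivor without progression, this drops the time between the last scan and the last contact. For a survivor who has progressed, the date is either undefined or lies before progression, so months of known survival are discarded. Patients who die keep their full time. The result is a one-sided loss of time at risk, linked to progression and therefore informative.

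OS is a secondary, descriptive endpoint. It still matters: the synopsis promises median OS and annual survival rates, section 12.5.2 promises the median and monthly rates, and section 12.4 looks to the secondary endpoints when judging whether the treatment is promising. An unclear rule also leaves the censoring date open to choice after the data are seen.

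**Working it through.** **1. The texts side by side**

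| Place | Date or evidence used |
|---|---|
| 11.2.4, survivors | PFS date, i.e. last progression-free imaging (11.2.2) |
| 11.2.4, parenthesis | survival, confirmed by telephone if need be |
| 11.2.4, lost to follow-up | last day known alive |
| 11.2.2, PFS date | imaging; telephone alone refused; only survivors not progressed |
| Table 8.1 | last day known alive is collected |
| 8.7 | outcome followed to death or end of study |

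A telephone call can show that a patient is alive; it cannot supply a clean scan. Read literally, a progressed patient who is lost keeps follow-up to last contact, while one known to be alive has no date or an earlier one.

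**2. Direction**

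Kaplan-Meier: S(t) = product over death times t_j ≤ t of (1 − d_j/n_j). Moving survivors' censoring earlier leaves every d_j unchanged and can only reduce n_j. Each factor stays equal or falls, so S(t) stays equal or falls.

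**3. Size (assumed survival)**

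The plan states no OS figure to reproduce. Inputs:
- Median PFS 5.6 months (pembrolizumab plus ramucirumab, section 2.7), with median OS set at 9 or 12 months. Section 2.2 puts median OS below 12 months.
- PFS 6.6 and OS 20.8 months (pembrolizumab plus 5-FU plus cisplatin, section 2.7), an optimistic case.
- Uniform accrual over 9 months (2.10.3).
- Cut-off 12 months after last enrolment (12.4) or 24 months (8.7).
- Scans at weeks 6, 12, 18, 24, 33, 42, then every 12 weeks (8.6).

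Model: exponential time to progression with rate λ1 = ln 2 / median PFS, then exponential survival after progression with rate λ2, chosen so that at the assumed median OS

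S(t) = (λ2·e^(−λ1·t) − λ1·e^(−λ2·t)) / (λ2 − λ1) = 0.5.

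For PFS 5.6 / OS 12: λ1 = 0.693/5.6 = 0.1238 and λ2 = 0.1595 per month. Check: (0.1595 × 0.2264 − 0.1238 × 0.1476)/0.0357 = 0.50.

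Rules, on 400,000 simulated patients per case:
- (a) survivors censored when last known alive;
- (b) all survivors at the last progression-free scan;
- (c) as (b), but progressed survivors run to the cut-off.

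| PFS / OS | Cut-off (months) | Median OS, (a) to (b) | 12-month OS, (a) to (b) |
|---|---|---|---|
| 5.6 / 9 | 12 | 9.0 to 8.9 | 36% to 34% |
| 5.6 / 9 | 24 | no visible change | no visible change |
| 5.6 / 12 | 12 | 12.0 to 10.9 | 50.0% to 43.4% |
| 5.6 / 12 | 24 | 12.0 to 11.9 | 50.1% to 49.3% |
| 6.6 / 20.8 | 12 | 20.7 to 14.3 | 74.4% to 63.8% |
| 6.6 / 20.8 | 24 | 20.8 to 17.5 | 74.4% to 70.7% |

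In the 5.6 / 12 case at 24 months, 24-month OS also falls, from 15.4% to 11.5%. Repeat runs agree to about 0.1 month and 0.6 points.

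Under (c) the effect is small: at the 12-month cut-off, 12-month OS goes from 50.0% to 49.8% in the 5.6 / 12 case, and the median from 20.7 to 19.9 in the 6.6 / 20.8 case (unchanged at 24 months). Progressed survivors are what matters: at the 12-month cut-off they are about 20% of patients in the 5.6 / 12 case and 43% in the 6.6 / 20.8 case.

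**4. At the trial's size (29 patients, PFS 5.6 / OS 12, 4,000 trials per cell)**

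- 12-month cut-off: mean 12-month OS 50.1% to 42.9%; a loss of at least 5 points in 70% of trials.
- 24-month cut-off: 49.9% to 49.0%; such a loss in 1% of trials.
- OS was never higher under (b).
- Sampling SD for comparison: √(0.5 × 0.5/29) = 0.093, about 9 points.

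**5. Sensitivity**

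- Adding 15% deaths without progression gives medians of 12.0 to 10.7 (12-month) and 12.0 to 11.7 (24-month) in the 5.6 / 12 case.
- The synopsis and Tables 8.2 and 8.6 give six-weekly scans. With PFS 5.6, OS 11.4 and the 12-month cut-off, 12-month OS under (b) is 42.1% with six-weekly scans and 41.6% with the 8.6 schedule, against 47.3% under (a).

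**The case against.** The strongest reply is that this is a drafting slip with an obvious intended meaning. The telephone parenthesis, the sentence on lost patients, Table 8.1 and section 8.7 all point to last known alive, and the separate SAP may already say so. The larger losses also need rule (b), which extends the PFS date to progressed patients although 11.2.2 does not define it for them. They further need either the shorter cut-off or an optimistic OS taken from a different regimen. With 24 months of follow-up and OS of 9 to 12 months, the change in 12-month OS is at most 0.8 points, well inside sampling error. Section 12.4 sets no formal development criteria, no OS test or threshold is stated, and the bias cannot flatter the treatment.

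Most of this stands, and it limits the size. It does not remove the defect. The survivor sentence covers every surviving patient without exempting those who have progressed, and no text shown corrects it. The 12-month cut-off is the one section 12.4 attaches to the final analysis. A SAP that elaborates this text should not have to contradict it.

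**Conclusion.** The concern holds. Section 11.2.4 names a date that conflicts with its own parenthesis, with the next sentence and with the data to be collected, and that is undefined for patients alive after progression. The contradiction and the downward direction are certain.

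The size is not, because it rests on assumed survival, an exponential model, the cut-off and the treatment of progressed survivors. If they are cut back to the last clean scan, the loss in the cases tabulated runs from no visible change to 6.4 months in the median (20.7 − 14.3) and 10.6 points in 12-month OS (74.4 − 63.8). If they run to the cut-off, it is close to nil. The primary ORR analysis and the stage 1 rule are unaffected. This should be corrected before data fixation, but it does not threaten the trial's main conclusion.

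**What to change.** Replace the survivor sentence in 11.2.4 with: *Surviving patients are censored on the last day survival was confirmed (visit or documented telephone contact), up to the data cut-off.* Put the same rule in the separate SAP before data fixation. The cost is one protocol sentence and one SAP line. No new data are needed, since the dates are already collected under Table 8.1 and section 8.7.

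As a separate edit, reconcile the observation period, which sets the OS cut-off: it is 12 months or 1 year in 12.4 and 2.10.3, but 2 years in the synopsis and 8.7. That touches up to four places.
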